PCRC PROPOSAL COVER SHEET

Title of Study or Project:	Association Between Driving Pressure and Postoperative Outcomes in Non-Cardiac Surgery Patients
Primary Institution:	Memorial Sloan Kettering Cancer Center, New York, NY
Principal Investigator:	[name]
Co-Investigators:	[name] [name] [name] [name]
Type of Study:	 Exploratory  Retrospective Observational  Prospective Randomized
IRB Number/Status:	Approved, IRB Exempt Protocol X18-028
Hypothesis:	Increased driving pressure during nonspontaneous mechanical ventilation will correlate with increased 30-day in-hospital mortality in a noncardiac surgery population
Number of Patients/Participants:	Estimated 85,000. (DataDirect query found 128,489 patients with 144,876 cases, and we estimate 1/3 loss of cases due to insufficient data.)
Power Analysis:	The primary hypothesis of interest is the effect of driving pressure in the presence of other covariates using multivariable logistic regression. We assume squared multiple correlation coefficient (R^2) of 0.3 to generate the variance inflation factor. Assuming an alpha of 0.05 and 10% event rate, an anticipated sample size of 85,000 will provide 95% power to detect an effect size of 0.049.
Proposed statistical test/analysis:	Multivariate logistic regression will be performed using the postoperative outcome of 30-day in-hospital mortality and driving pressure as the exposure to determine if an association exists. Secondary outcome analysis will focus on pulmonary complications defined by ICD 9/10 Codes. Variables including but not limited to age, gender, intubation time length, pulmonary disease, BMI, and ASA score will be analyzed.
Resources (Brief summary of resources for data collection, personnel, financial):	The MPOG database will be queried for the specified concept IDs with programmatic support from the MPOG Coordinating Center. Statistical analyses will be performed by biostatisticians from the MSKCC Department of Epidemiology & Biostatistics led by [name].

Introduction

What is the significance of the clinical problem being addressed?

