The primary exposure is driving pressure, recorded as the median of patient trajectory (continuous variable). The relationship between driving pressure and 30-day in-hospital mortality will be assessed with a multivariable logistic regression model, adjusting for preoperative and intraoperative factors. Confounders include but are not limited to age at surgery, gender, intubation time, ventilatory mode, airway device (i.e. endotracheal tube, LMA), pulmonary disease, BMI, ASA score. Potential non-linear relationship between driving pressure and the outcome will be examined using restricted cubic spline analysis. If a significant non-linear relationship between driving pressure and the outcome is detected, all subsequent analyses will include non-linear version of driving pressure. The non-linearity assumption will also apply to all other continuous variables across all analyses where appropriate.

If time to mortality is available, we will summarize the time to death (overall survival) as a survival endpoint using survival analysis approach: Kaplan-Meier curves to depict the pattern of survival over time and Cox proportional hazards model to assess the association between driving pressure and death adjusting for all relevant variables as done in the multivariable logistic model described above.

To address the second objective, the multivariable logistic regression model for 30-day mortality will include tidal volume in mL per kg of ideal body weight as well as its interaction with driving pressure, along with potential confounders. A significant interaction term will indicate that the relationship between tidal volume and 30-day mortality is moderated by driving pressure. The varying impact of the interaction between tidal volume and driving pressure on the probability of the primary outcome may be described graphically using quantiles of driving pressure.

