Similarly, we will assess the interaction between driving pressure and 3 specific factors on the primary outcome: (1) supraglottic air way devices (i.e., LMAs) vs endotracheal tubes, (2) laparoscopic cases vs non-laparoscopic, and (3) craniotomy vs non-craniotomy cases. A significant interaction term will indicate that the relationship between driving pressure and the outcome is modified by these specific factors. Subsequent subgroup analyses will be performed in each subgroup to identify the impact of driving pressure specifically within each subgroup (i.e., driving pressure has a much larger impact on 30-day mortality among craniotomy cases than those observed among non-craniotomy cases). As a sensitivity analysis, we will also perform the primary analysis after exclusion of emergency surgery cases.

Secondary outcomes include postoperative pulmonary complications (PPCs) within 30 days (presence of class 1, 2, or 3) and length of stay. PPCs will be analyzed using multivariable logistic regression, while length of stay will utilize Poisson regression. All models will include driving pressure as the variable of interest, adjusting for the same factors as in the primary analyses. As above, we will assess the interaction between driving pressure and tidal volume to investigate the presence of modification of the relationship between tidal volume and the outcome by the driving pressure.

The primary exposure variable (driving pressure) is defined as the median of patient driving pressure values collected intraoperatively. In an exploratory manner, we plan to investigate other methods to quantify driving pressure that is informative of the outcome and can provide clinical relevance. One alternative is to utilize the cumulative number of minutes with a driving pressure over 15 cmH₂O, based

on findings in acute respiratory distress syndrome patients.⁴ Another alternative is to consider the area under the curve (of the continuously measured driving pressure) for each patient.

Power analysis

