Ventilation Mode	Ventilation mode	String	Concept 3182 Ventilator Mode (most common for case)
Intubation Time	First Intubation time (as minutes)	Integer	Concept 50695 Categorized note Intubation

	from anesthesia start)		
Extubation Time	Last Extubation Time	Integer	Concept 50202 – Emergence Patient Extubated
Reversal Time	Time of administration of NMB reversal	Integer	Concept 10739 – Sugammadex Concept 10315 – Neostigmine Concept 10383 – Pyridostigmine
Median tidal volume	Median TV	Integer	Concept 3190 – Tidal Volume Actual
Median respiratory rate	Median respiratory rate	Integer	Concept 3580 – RR
Median peak inspiratory pressure	Median peak inspiratory pressure	Integer	Concept 3185 – PIP
Median plateau inspiratory pressure	Median plateau inspiratory pressure	Integer	Concept 3186 – Plateau IP
Median PEEP	Median Positive End Expiratory Pressure	Integer	Concept 3210 – PEEP Measured
Median EtCO ₂	Median end tidal carbon dioxide	Integer	Concept 3235 – EtCO ₂ (mmHg)
Median FiO ₂	Median Fraction of Inspired Oxygen	Integer	Concept 3200 – Ventilator FiO ₂ Measured
Mortality (days)	Days from Date of Surgery to Date of Death	Integer	Mortality Table
Pulmonary Complications	See Appendix for ICD Diagnosis codes associated with Pulmonary Complications		

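### The duration covariate is defined inconsistently: the cover sheet intends a length of intubation, but the variable table defines Intubation Time as minutes from anesthesia start to the tube

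*Protocol*

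**What the plan says.** Three places in the protocol describe what appears to be one covariate.

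- **Cover sheet, proposed statistical test/analysis:** "Variables including but not limited to age, gender, intubation time length, pulmonary disease, BMI, and ASA score will be analyzed". The item is a length.
- **Statistical analysis, primary model:** "Confounders include but are not limited to age at surgery, gender, intubation time, ventilatory mode, airway device", followed by pulmonary disease, BMI and ASA score. The word for length has gone, and the list is open-ended.
- **Variables to be collected:** the row *Intubation Time* is "First Intubation time (as minutes", and the cell goes on, after a layout break, to give anesthesia start as the origin. A separate row holds "Last Extubation Time", with no stated origin or unit. *Surgery Duration*, in minutes, is also collected but is not named as a confounder.

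The Statistical analysis section carries the primary model's factors into the Cox model and into the models for postoperative pulmonary complications (PPCs) and length of stay.

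The primary exposure is the per-case median driving pressure. Two further exposures are offered as exploratory: "cumulative number of minutes with a driving pressure over 15 cmH₂O", and "Another alternative is to consider the area under the curve (of the continuously measured driving pressure) for each patient". Neither is divided by ventilated time. Eligibility requires at least two hours of ventilation and sets no upper limit.

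**The concern.** An analyst who matches the model's list to the variable table by name will enter the minutes from anesthesia start to the tube. That quantity says nothing about how long the patient was then ventilated. No other item in the named set is a duration.

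The protocol itself treats duration as relevant. It justifies the two-hour minimum by the need for enough exposure to affect the primary outcome. If longer cases also carry higher mortality, more PPCs or longer stays (an assumption; the document gives no figures), two things follow:

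- In the median-exposure models, duration is a potential confounder that the named set does not address.
- In the exploratory models, the exposure itself grows with ventilated time. Any association between duration and outcome would then appear as an association with driving pressure.

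There is also a practical consequence. Supraglottic-airway cases are included and form a planned interaction group, yet they may have no intubation note. If so, the covariate would be missing for them, and the planned complete-case analysis could drop them.

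**Working it through.** The protocol states no figure on this point, so there is none to reproduce. The check is a comparison of text, followed by short arithmetic on the cumulative exposures.

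**1. The covariate across the three places**

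| Place | Term | Kind of quantity |
|---|---|---|
| Cover sheet | intubation time length | duration |
| Primary model | intubation time | ambiguous |
| Variable table | minutes from anesthesia start to first intubation | clock position |

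The first and third rows cannot both describe the covariate. The second can be read either way, and the only definition it can be matched to by name is the third.

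**2. Can a duration be built from collected fields?** Yes: last extubation minus first intubation. But the protocol never states this subtraction, and the extubation row gives no origin or unit, so a common origin has to be specified first.

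**3. How the area under the curve (AUC) depends on time.** With constant pressure, AUC = driving pressure × ventilated minutes. The patients below are invented to show the scaling.

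- 10 cmH₂O for 8 h: 10 × 480 = 4,800 cmH₂O·min.
- 20 cmH₂O for 2 h: 20 × 120 = 2,400 cmH₂O·min.
- Ratio: 4,800 / 2,400 = 2, so the patient at half the pressure is ranked as twice as exposed.
- Same pressure, 8 h against 2 h: 480 / 120 = 4.

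**4. How far each cumulative exposure tracks duration.** This depends on spreads that the document does not give. A simulation used these assumptions, none of them from the protocol:

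- ventilated duration at least 120 min, mean 240 min, coefficient of variation 0.3 to 0.6;
- driving pressure log-normal between patients, centred on 9, 12 or 15 cmH₂O, coefficient of variation 0.2 to 0.4;
- within-case SD 2 cmH₂O;
- pressure independent of duration.

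| Exposure | Spearman with duration | Spearman with driving pressure |
|---|---|---|
| AUC | 0.53 to 0.85 | 0.47 to 0.82 |
| Minutes above 15 cmH₂O | 0.05 to 0.36 | 0.90 to 1.00 |

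Duration carried 32% to 81% of the variance of log AUC. AUC is therefore substantially tied to time over the whole range tried. Minutes above 15 cmH₂O mainly followed pressure, although for a patient above the threshold throughout, the count equals ventilated time.

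**5. Is the protocol's count of ventilator minutes a usable duration?** Not as printed. Exposure Variables keeps only minutes with PIP − PEEP ≤ 6. Driving pressure is plateau minus PEEP. If plateau does not exceed PIP (an assumption), every retained minute has driving pressure ≤ 6 cmH₂O. A count built on that condition would be tied to the exposure it is meant to be separated from.

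**The case against.** The strongest reply is that the variable table lists mostly raw fields and not finished covariates. BMI is in the model, but the table holds only height and weight. Airway device appears as separate tube-type and LMA-type rows. Driving pressure itself has no row. On that pattern, *Intubation Time* and *Extubation Time* are simply the two ends of an intubation length, and the missing-data section uses the same two ends to bound the medians. The cover sheet shows that a length is meant, the confounder list is expressly open, Surgery Duration is collected, and final covariate coding may sit in an analysis plan that is not shown.

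Much of this stands. A reader might infer that exposure duration is uncontrolled. The document does not support that, because it shows an intention to include a length and collects the means to do so. What remains is that the named model term matches a row with a different, explicit definition and that no derivation is given. An open list permits the correction but does not make it.

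A reader might also infer that both cumulative exposures largely measure operation length. That is not shown either. It depends on unstated spreads for AUC, and it fails for minutes above 15 cmH₂O in the illustration.

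It is also fair to say that a cumulative dose is meant to grow with time, that both measures are exploratory, and that a time-weighted mean would come close to the existing median. The remedy therefore does not replace AUC; it asks for duration in the model.

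**Conclusion.** The point holds as an inconsistency in a stated definition. Read literally, the protocol puts time-to-tube into the primary, Cox, PPC and length-of-stay models and names no ventilation or surgery duration.

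For the primary analysis the size is unknown. The median does not accumulate with time, so bias would need duration to be related both to median driving pressure and to the outcome, and the document quantifies neither. For the exploratory measures, the dependence on time is arithmetical: four-fold in AUC between a 2-hour and an 8-hour case at equal pressure. How much of the between-patient variation this explains rests on the assumed spreads above. The document supports neither the conclusion that duration will be left out nor the conclusion that the cumulative measures are mostly operation length.

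This should be corrected before the models are run. It does not undermine the design.

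**What to change.** - In the primary model's confounder list and in the variable table, define the covariate as ventilated duration: last extubation minus first intubation, both in minutes from one stated origin. Where there is no tube time, for example with supraglottic airways, use Case Start to Case End as the protocol already defines them.
- Enter it in every model, with non-linearity allowed, as the protocol already provides for continuous variables.
- Do not use the count of qualifying ventilator minutes as the duration until its printed PIP − PEEP condition has been reconciled.
- Report AUC and minutes above 15 cmH₂O only from models that contain this duration. The percentage of ventilated minutes above 15 cmH₂O may be added.

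The cost is wording; the time fields are already on the collection list. The one statistical price is that, given duration, the cumulative measures have less independent spread, so their intervals will be wider.

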Appendix: ICD Diagnosis Codes Associated with Pulmonary Complications

Based on Douville study under review for publication.

Class 1 Pulmonary Complications

514	Pulmonary congestion and hypostasis
518.7	Transfusion related lung injury (TRALI)
997.3	Respiratory complications not elsewhere classified
997.31	Ventilator associated pneumonia
997.32	Postprocedural aspiration pneumonia
997.39	Other respiratory complications
J95.84	Transfusion related lung injury (TRALI)
J95.851	Ventilator associated pneumonia
J98.9	Respiratory disorder, unspecified
J95.859	Other complication of respirator
J95.88	Other intraoperative complications of respiratory system, not elsewhere classified
J95.89	Other postprocedural complications and disorders of respiratory system, not elsewhere classified

Class 2 Pulmonary Complications

480*	Viral pneumonia
481*	Pneumococcal pneumonia
482*	Other bacterial pneumonia
483*	Pneumonia due to other specified organisms
484*	Pneumonia in infectious diseases classified elsewhere
485*	Bronchopneumonia, organism unspecified
486*	Pneumonia, organism unspecified
506	Respiratory conditions due to chemical fumes and vapors
506.1	Acute pulmonary edema due to fumes and vapors
506.2	Upper respiratory inflammation due to fumes and vapors
506.3	Other acute and subacute respiratory conditions due to fumes and vapors
507*	Pneumonitis due to solids and liquids
512*	Pneumothorax and air leak
518.1	Nontraumatic subcutaneous emphysema
518.4	Acute edema of the lung, unspecified
518.5	Pulmonary insufficiency following trauma and surgery
518.51	Acute respiratory failure following trauma and surgery
518.52	Other pulmonary insufficiency, not elsewhere classified, following trauma and surgery
518.53	Acute and chronic respiratory failure following trauma and surgery
518.81	Acute respiratory failure
518.82	Other pulmonary insufficiency, not elsewhere classified
786.09	Respiratory Insufficiency
799.1	Respiratory arrest
J12*	Viral pneumonia, not elsewhere classified
J13*	Pneumonia due to Streptococcus pneumoniae
J14*	Pneumonia due to Hemophilus influenzae

J15* Bacteria pneumonia, not elsewhere classified
 J16* Pneumonia due to other infectious organisms, not elsewhere classified
 J17 Pneumoniae in diseases classified elsewhere
 J18* Pneumonia, unspecified organism
 J68.0 Bronchitis and pneumonitis due to chemicals, gases, fumes and vapors
 J68.1 Pulmonary edema due to chemicals, gases, fumes, and vapors
 J68.2 Upper respiratory inflammation due to chemicals, gases, fumes, and vapors, not elsewhere classified
 J68.3 Other acute and subacute respiratory conditions due to chemicals, gases, fumes, and vapors
 J68.4 Chronic respiratory conditions due to chemicals, gases, fumes, and vapors
 J68.8 Other respiratory conditions due to chemicals, gases, fumes, and vapors
 J68.9 Unspecified respiratory conditions due to chemicals, gases, fumes, and vapors
 J85.1 Abscess of lung with pneumonia
 J69.0 Pneumonitis due to inhalation of food and vomit
 J80 Acute respiratory distress syndrome
 J81.0 Acute pulmonary edema
 J93* Pneumothorax and air leak
 J95.811 Postprocedural pneumothorax
 J95.812 Postprocedural air leak
 J95.821 Acute postprocedural respiratory failure
 J95.822 Acute and chronic postprocedural respiratory failure
 J96.0 Acute respiratory failure
 J96.00 Acute respiratory failure, unspecified whether with hypoxia or hypercapnia
 J96.01 Acute respiratory failure with hypoxia
 J96.02 Acute respiratory failure with hypercapnia
 J96.1 Chronic respiratory failure
 J96.10 Chronic respiratory failure, unspecified whether with hypoxia or hypercapnia
 J96.11 Chronic respiratory failure, with hypoxia
 J96.12 Chronic respiratory failure, with hypercapnia
 J96.2 Acute and chronic respiratory failure following trauma and surgery
 J96.20 Acute and chronic respiratory failure unspecified whether with hypoxia or hypercapnia
 J96.21 Acute and chronic respiratory failure with hypoxia
 J96.22 Acute and chronic respiratory failure with hypercapnia
 J96.9 Respiratory failure, unspecified
 J96.90 Respiratory failure, unspecified whether with hypoxia or hypercapnia
 J96.91 Respiratory failure, unspecified with hypoxia
 J96.92 Respiratory failure, unspecified with hypercapnia
 R09.0 Asphyxia and hypoxemia
 R09.01 Asphyxia
 R09.02 Hypoxemia
 R09.2 Respiratory arrest
 S27.0 Traumatic pneumothorax

Class 3 Pulmonary Complications

415.1 Pulmonary embolism and infarction
 415.11 Iatrogenic pulmonary embolism and infarction
 415.12 Septic pulmonary embolism

415.19 Other pulmonary embolism and infarction
415.3 Pulmonary embolism and infarction, episode of care unspecified
487* Influenza
488* Influenza due to certain identified influenza viruses
799* Cerebral asphyxia/suffocation/asphyxia/hypoxia
998.81 Surgical subcutaneous emphysema
958.7 Traumatic subcutaneous emphysema
I26.0 Pulmonary embolism with acute cor pulmonale
I26.01 Septic pulmonary embolism with acute cor pulmonale
I26.02 Saddle embolus of pulmonary artery with acute cor pulmonale
I26.09 Other pulmonary embolism with acute cor pulmonale
I26.9 Pulmonary embolism without acute cor pulmonale
I26.90 Septic pulmonary embolism without acute cor pulmonale
J09* Influenza due to certain identified influenza viruses
J10* Influenza due to other identified influenza virus
J11* Influenza due to unidentified influenza virus
R06.4 Hyperventilation
R09.1 Pleurisy
R09.3 Abnormal sputum
R09.8 Other specified symptoms and signs involving the circulatory and respiratory systems
T79.7 Traumatic subcutaneous emphysema

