- 1) Investigate the association of driving pressure and 30-day in-hospital mortality in nonspontaneous mechanically ventilated non-cardiac surgical patients undergoing two lung ventilation.
- 2) Investigate the association of tidal volume in mL per kg IBW with 30 day in-hospital mortality and how this relationship is modified by driving pressure
- 3) Subgroup analysis: There are several patient subgroups that may play a role in modifying the association between driving pressure and mortality:
 - Pulmonary pressure using supraglottic airway devices (i.e. LMA's) may not be identical to endotracheal tubes given that the physiology is slightly different. We will analyze these two groups to determine if how the association to outcomes are modified.
 - Laparoscopic cases have increased extra-thoracic pressures on the lung due to insufflation which may not be analogous to increased pulmonary pressures due to ventilatory strategies.
 - Craniotomy cases sometimes are managed with hyperventilatory strategies to decrease intracranial pressures through hypocapnia. These hyperventilatory strategies may cause increased pulmonary pressure that is different from other types of cases and should be examined separately.
- 2) Secondary objective: Investigate the association of driving pressure and postoperative pulmonary complications within 30 days (presence of class 1, 2, or 3), and also length of stay.

Methods

Study Database and Population

MPOG is a non-profit academic consortium analyzing perioperative outcomes from hospitals in 18 states and 2 countries. Using electronic records including over 8.2 million anesthetic cases, MPOG facilitates analysis of the critical factors we are investigating regarding intraoperative respiratory variables and postoperative outcomes.

IRB statement

The project has been approved by the Memorial Sloan Kettering Cancer Center IRB under protocol X18-028.

Exposure Variables

- **Case Start:**
 1. Anesthesia Induction End (Concept 50005). If not available, then
 2. Anesthesia Induction Begin (Concept 50004). If not available, then
 3. Procedure Start (Concept 50006). If not available, then
 4. Patient in Room (Concept 50003). If not available, then
 5. Anesthesia Start (Concept 50002).
- **Case End:**
 1. Patient Extubated (Concept 50202). If not available, then
 2. Procedure End (Concept 50007). If not available, then
 3. Patient Out of Room (Concept 50008). If not available, then
 4. Anesthesia End (Concept 50009).

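### The postoperative pulmonary complication endpoint counts J95.88, a code labelled intraoperative, with no onset rule, so for that code exposure is not shown to precede outcome

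*Protocol*

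**What the plan says.** **Endpoint.** The Protocol's Statistical analysis section states: "Secondary outcomes include postoperative pulmonary complications (PPCs) within 30 days (presence of class 1, 2, or 3) and length of stay". One code from any class makes a patient a case. The specific goals use the same definition.

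**Code list.** Class 1 in the ICD appendix includes J95.88, "Other intraoperative complications of respiratory system, not elsewhere classified". The next line is J95.89, "Other postprocedural complications and disorders of respiratory system, not elsewhere classified". The appendix thus separates the two periods and then counts both.

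**Exposure.** In Statistical analysis: "The primary exposure variable (driving pressure) is defined as the median of patient driving pressure values collected intraoperatively". The section on missing data and artifacts limits the values entering the medians to those between intubation and extubation.

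**Timing.** No passage requires onset after the case ends, cuts the pressure record at an event, or plans a PPC analysis without J95.88. The pulmonary complications row under Variables to be collected refers only to the diagnosis codes. Under Secondary outcomes, the classes are said to reflect how likely the cause lies in anesthetic ventilator management, which is not a timing criterion.

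**The concern.** An exposure–outcome odds ratio is easiest to interpret when the exposure is complete before the outcome occurs. A J95.88 event, by its label, happens during the operation over which the exposure is being measured. The Introduction defines driving pressure as tidal volume divided by respiratory-system compliance. At a given tidal volume, an event that lowers compliance therefore raises driving pressure. If that happens and persists, the whole-case median includes values that the event produced, and the same event is scored as the outcome.

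Such a bias would run in the hypothesised direction. Adjusting for the listed confounders would not remove it, because it arises from the order of events and not from a common cause. What is at stake is whether a positive PPC result can be read as driving pressure coming before lung complications.

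**Working it through.** The protocol states no figure for the PPC endpoint, so there is none to reproduce. The check has two parts.

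**1. Order of events, from the text**

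| Element | Period | Place in Protocol |
|---|---|---|
| Median driving pressure | intubation to extubation | Statistical analysis; Handling of missing data and artifacts |
| J95.88 | intraoperative, by its label | ICD appendix, Class 1 |
| J95.89 | postprocedural, by its label | ICD appendix, Class 1 |
| PPC endpoint | postoperative, within 30 days | Specific goals; Statistical analysis |

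J95.88 does not fit the endpoint's name and overlaps the exposure period. J95.89 fits. The overlap shows that the order is not secured. It does not show which came first.

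**2. Possible size**

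Inputs:
- n = 85,000 (Protocol, Power analysis).
- s, the share of PPC cases that are J95.88 events, and d, their upward shift in median driving pressure in SD: **assumed**.
- PPC rate p = 10% or 5%: **assumed**. The Power analysis uses these rates for 30-day mortality and gives none for PPCs.

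Model: no true effect; non-cases N(0,1); cases a mixture of (1 − s) N(0,1) and s N(d,1). The mean difference between cases and non-cases is s × d, so the fitted log odds ratio per SD is about s × d. The standard error is about 1/√(n p (1 − p)):
- p = 10%: 1/√(85,000 × 0.09) = 1/√7,650 = 0.0114
- p = 5%: 1/√(85,000 × 0.0475) = 1/√4,037.5 = 0.0157

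The two-sided rejection rate at nominal 5% is Φ(k − 1.96) + Φ(−k − 1.96), with k = s × d / SE.

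| s | d | s × d | Odds ratio per SD | Rejection, p = 10% | Rejection, p = 5% |
|---|---|---|---|---|---|
| 0.5% | 0.5 | 0.0025 | 1.003 | 5.5% | 5.3% |
| 0.5% | 1 | 0.005 | 1.005 | 7% | 6% |
| 1% | 0.5 | 0.005 | 1.005 | 7% | 6% |
| 1% | 1 | 0.010 | 1.010 | 14% | 10% |
| 5% | 1 | 0.050 | 1.051 | 99% | 89% |

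Solving the logistic score equations numerically on a grid gives the same slopes (0.0025, 0.0050, 0.0100 and 0.0498 at p = 10%).

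These are unadjusted values. If the shift is unrelated to the covariates and those explain R² = 0.3 of driving pressure (the Power analysis value), the adjusted coefficient is about s × d/(1 − R²). For the fourth row that is 0.010/0.7 = 0.014. Under that assumption adjustment enlarges the bias slightly.

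The last row shows how the bias grows. It is not an estimate for J95.88.

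**The case against.** The strongest counter-argument is that the text shows overlap in time and not direction. High driving pressure may itself cause an intraoperative event, and the list was built around ventilator-related etiology. The stated aim is also only an association. This stands against the stronger reading a reader might infer, that reverse causation is built into the PPC odds ratio. The documents do not say that a J95.88 event lowers compliance or that its effect lasts. It does not rescue the code: whichever way causation runs, the event is not postoperative, and the whole-case median can include values recorded after it.

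The size is also open to challenge. J95.88 is one code in a long composite that includes pneumonia, respiratory failure, hypoxemia and embolism. Patients need at least two hours of ventilation, so a brief or late event moves a median little, and d = 1 needs an early, sustained one. This stands. A reader might also set the 0.050 in the last row beside the 0.049 in the Power analysis, but that detectable effect is for mortality.

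A reader might extend the point to 998.81, "Surgical subcutaneous emphysema", because the specific goals say: "Laparoscopic cases have increased extra-thoracic pressures on the lung due to insufflation". That label fixes no timing, and the link described would be confounding by laparoscopy. Laparoscopy is a collected variable and the confounder list is open. The documents do not support deleting 998.81 on this ground.

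Finally, how codes are dated may be left to an analysis plan that is not at hand. That covers an onset rule, but not a code list that the protocol itself fixes and that contradicts its own endpoint.

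**Conclusion.** The point holds as a contradiction within the protocol. A code labelled intraoperative counts toward a postoperative endpoint, its period overlaps the exposure measurement, and nothing requires onset afterwards. For J95.88, reverse causation cannot be excluded. That it occurs is not shown.

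The bias is about s × d on the log odds ratio per SD. For J95.88 alone it is probably small: 0.0025 to 0.01 if s is 0.5–1% and d is 0.5–1, an odds ratio of roughly 1.003 to 1.010. This rests on assumed s and d, and the rejection rates also on assumed PPC rates. Only the secondary PPC outcome is affected; 30-day in-hospital mortality and length of stay are not. The change is worth making because the contradiction is plain and the correction is cheap.

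**What to change.** 1. Remove J95.88 from the PPC endpoint and keep J95.89. Report the PPC result with J95.88 included as well, for comparability with the source list.
2. Removing one code does not settle timing, because other listed codes cannot be timed from their labels (for example 997.39, 512*/J93*, J95.84 and 998.81). Refit the PPC model once, as a fixed sensitivity analysis, with driving pressure taken as the median over an early window of controlled ventilation. Set the window length before the data are examined. The first 60 minutes is one workable choice: inclusion requires two hours of ventilation and a plateau pressure at least every five minutes, which gives about 60/5 = 12 values per patient.
3. State in advance that driving pressure will not be said to precede the complication if the association appears only with the whole-case median.

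**Cost:** one line of the appendix, one comparison and one extra model on intraoperative values already needed for the median. The downside is a few fewer PPC events and a noisier exposure in the sensitivity analysis.
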